3.1. Methods, analyses and technologies

The adoption of a mixed methods design is pivotal for a comprehensive exploration of the feasibility and potential challenges associated with a larger-scale randomized controlled trial (RCT) of the effects of an intervention (28). **Employing multiple perspectives allows for a more complete understanding and facilitates a nuanced assessment of the acceptability of the TYSB intervention.** It is crucial to incorporate the voices of sexually traumatized women and their eventual partners when the research project focuses on a treatment intervention to which they are subjected (29). A mixed methods study employs both qualitative and quantitative methods to collect and analyze data, as well as to organize procedures for investigating research questions. We have described the study design in Figure 1.

Recruitment of participants

To gain access to data that can shed light on the research questions, two groups will be conducted according to the TYSB intervention described above, each consisting of ten women (N=20). We will recruit participants from patients referred to specialized mental health care and the TYSB intervention at STHF. The recruitment process follows standard clinical practice to ensure the selection of appropriate participants for the study. *Inclusion criteria:* a) A history of sexual trauma, b) Experience trauma-related sexual problems, c) Age between 18 and 65 years, d) Enough competence in Norwegian to participate in a psychoeducational group. *Exclusion criteria:* a) Acute suicidality, b) Serious substance abuse interfering with treatment, c) Severe dissociative or psychotic disorders, d) Current life crisis interfering with treatment e) Living in an abusive relationship.

Data collection

Study A and study B: These are qualitative studies where we collect data from exploratory semi-structured in-depth interviews with participants (including possible dropouts) and partners post intervention. We will use interview guides to provide a framework to ensure that all participants are asked about the same core topics.

Study C: This is an explanatory sequential mixed methods study where we collect and analyze quantitative data from self-report forms and physiological measurements pre-post and 3- month follow-up, followed by collecting and analyzing qualitative data from semi-structured in-depth interviews with participants, focusing on how they understand quantitative data that stands out or are experienced as unexpected. Finally, we interpret how qualitative data can explain the quantitative data.

Self-report measurements: *The international trauma questionnaire (ITQ)* is a well-validated instrument that assess symptoms of post-traumatic stress disorder (PTSD) and complex PTSD (CPTSD) (30); *The Sexual Satisfaction Scale for Women (SSS-W)* is a widely used instrument with good psychometric properties designed to measure sexual satisfaction among women (31); *Sexual shame Index-revised (SSI-R)* is a 10-item scale used to measure sexual shame. Cronbach's alpha has been shown to range from 0.76 to 0.82, indicating an acceptable level of internal consistency for the SSI-R (32); *Multidimensional Assessment of Interoceptive Awareness (MAIA 2)* is a measure with robust psychometric properties, designed to assess interoceptive awareness, which is the ability to perceive internal bodily

signals (33); *Touch Body Map* is an instrument for mapping how the body reacts to touch, which is used in the TYSB intervention to deepen the reflection around personal experiences of touch (34). Participants color the outlines of a human figure with three colors to mark how different areas of the body react to touch. The body map gives a non-verbal expression of how trauma is embodied. The percentage of the different colors will be calculated to assess possible changes through the process; *Responses to script driven imagery (RSDI)* is an assessment tool to measure self-reported emotional, cognitive, and physiological responses in the script-driven imagery procedure (SDI) described below (35).

Physiological measurements: *Cardiovascular measurement (ECG)* recorded during a *script-driven imagery (SDI)* can give valuable and complementary data when investigating treatment response in trauma patients (36, 37). A 'Root mean square of successive differences of adjacent inter-beat intervals' (RMSSD) reflecting Heart Rate Variability (HRV) will be used to index changes in cardiac vagal tone. HRV is influenced by the balance between sympathetic and parasympathetic nervous system activity and can give information about perceived stress and emotional regulation. *Sample Entropy (SampEn)* is a measure of cardiac entropy, which can give information beyond linear HRV. Lower SampEn has been linked with psychopathology while a higher value of SampEn indicates a less regular, more complex signal fine-tuned to the needs of the internal and external environment (38).

Script-driven Imagery procedure (SDI)

This study will use a modified protocol of the original script-driven imagery procedure (35), described by Rudstam et al. (39). Participants will be instructed to write down two memories, one traumatic and one peaceful. The main researcher then prepares two scripts of three minutes each, based on participants' texts. The physiological measurements will be done approximately one week later, after participants have completed the self-rating scales. The main researcher read the two scripts aloud in the following order: 5 min. relaxation baseline (BL) – 3 min. peaceful memory script – 3 min. break – 3 min. trauma script – 3 min break – 3 min. peaceful memory script – 3 min break. Following the psychophysiological recording, the participants will complete the RSDI questionnaire.

Data from journal: The following data will be collected from the intake interview, documented in participants' journal; age, marital status, type and extent of sexual trauma and other relational traumas, degree of support after trauma(s), prior treatment exposure, sexual problems and current social support network.

[figure not shown]
Data analysis

Qualitative data analysis (study A, study B and the qualitative part of study C): Qualitative data will be analyzed using Giorgi's descriptive phenomenological method: (1) reading descriptions to grasp the whole, (2) dividing into meaning units, (3) identifying invariant, general meanings in psychological terms, and (4) synthesizing them into a general meaning structure (40). To ensure that the results are reliable, valid and credible, both supervisors will read all the interviews, critically assess the PhD candidate's analysis, and discuss and resolve any discrepancies in interpretation.

Quantitative data analyses (study C):

Quantitative data will be analyzed through linear mixed model analysis (procedure MIXED in SPSS) for statistical comparison of pre-post and follow-up changes in psychometric variables and physiological reactivity. Paired samples t test (two-tailed) will be used for statistical comparison. Due to the small sample size and explorative nature of the study, no statistical correction for multiple testing will be applied. To ensure a 95% confidence interval, analyzes will be performed with a bootstrapping technique. Missing responses will be handled through multiple imputation techniques. Overall significance level set at .05.

Figure 1: The projects study design

The doctoral thesis will utilize collected data and results to draw comprehensive conclusions about the TYSB interventions overall feasibility and associated risks and complications. These conclusions will inform the design of a future RCT, including power calculations, as well as primary outcomes, generating hypotheses, and providing insights into necessary modifications to optimize the TYSB intervention and its protocol, thereby improving validity and reliability.

Potential weaknesses and risks

We recognize the potential risk of participant drop-out. To ensure enough participants there will be conducted an interim analysis post intervention. A third group will be included in autumn 2026 if there is a larger dropout of women (>3) or less partners (<10) than expected or if the interim analysis reveals that a larger N is needed for designing an adequately powered future study. A potential source of bias in this study stems from the dual role of the PhD candidate, who is also developer of the treatment intervention. This overlap can introduce bias, affecting the impartiality of the study. To mitigate these risks, several strategies have been implemented: Independent therapists conduct the intervention groups, eliminating direct involvement from the researcher. In *studies A* and *B*, interviews are conducted by a co-researcher and user participant unconnected to the intervention, safeguarding impartial data collection and encouraging honest feedback. The analysis of the qualitative data will be done by the PhD candidate in close collaboration with the main supervisor and the co-supervisor who have no connection to the development of the

intervention and no financial interests in the project. It is considered that the PhD candidate's in-depth knowledge of both the intervention and the topic will strengthen the quality of the analysis. The independent supervisors will thoroughly review all interviews, offering new perspectives and critical reflections. They will validate and challenge methodological choices throughout the entire process to ensure that the results are reliable, valid, and credible. Statistical analyzes of the quantitative data will be carried out by the main supervisor in collaboration with an independent statistician at STHF, who has no connection to the intervention. Quantitative data from the questionnaires will be compared with objective physiological measures and participants own understanding of the results. This triangulation of data sources helps to strengthen the dataset and offers a more robust and unbiased objective assessment of the feasibility and acceptability of the intervention. Collectively, these strategies are essential for ensuring the study's reliability and reducing the likelihood that results will be influenced by the researcher's personal interests or expectations.

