Trauma patients exhibit a wide range of symptom profiles, making it essential to evaluate appropriate measures for assessing treatment outcomes (26). This heterogeneity is evident in the varying patterns of neural activation observed among patients. Incorporating physiological measurements provides objective indices to investigate treatment responses more accurately (27). **The complexity of trauma-related symptoms cannot be fully captured through quantitative data alone and there is a need to assess a more comprehensive understanding of treatment outcomes (26). Employing a mixed methods design that includes participants' own interpretations and understandings of quantitative results adds significant value and is a novel contribution to the research community (28).** Given the centrality of personal meaning in recovery-oriented practice, our application of a phenomenological perspective in researching this treatment represents a significant innovation (29).

2. Hypotheses, aims and objectives

The overall goal of this project is to ensure the quality of the novel TYSB intervention and lay the ground for a larger-scale RCT of the intervention. The project's overall goal is dispersed into three main aims, each in correspondence with a sub-study (study A, B and C):

Aim 1 (Study A): To investigate the lived experiences of participants in the intervention groups to evaluate the acceptability of the TYSB intervention and identify modifications required to improve the intervention.

Research question (RQ1): What are the participants lived experiences and perceptions of the intervention, and how do they react to any positive or negative impacts attributed to it?

Aim 2 (Study B): To explore the experiences and perspectives of partners of the participants in the intervention groups, with the aim of identifying areas for potential improvement in the intervention and specifically how partners can best be involved in the rehabilitation process.

RQ2: What are the partners' experiences of participating in the intervention and of being witness to and taking part in their partners (participants) process during the intervention?

Aim 3 (Study C): To establish foundational data, methodologies, and effect sizes for a subsequent full-scale RCT.

RQ3: What are the changes in patient-reported levels of PTSD symptoms, sexual satisfaction, sexual shame, interoceptive awareness and reactions to touch from pre intervention to post-intervention and at a 3-month follow-up?

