RQ4: How do the capabilities for regulating the autonomic nervous system measured by cardiovascular measurement (ECG) during a script-driven imagery (SDI) procedure change from before to after treatment and at follow-up?

RQ5: What is the adherence rate (recruitment, dropout, and attendance rates among participants) to the intervention?

RQ6: How do the participants interpret and reflect on the quantitative data collected at pre-post intervention and follow-up, with a specific focus on data that stands out or are unexpected in relation to their lived experiences?

Hypothesis (H1): Measurements will show improvements in PTSD symptoms, sexual satisfaction, sexual shame, interoceptive awareness and capability to enjoy touch after the intervention and at follow-up compared to baseline.

H2: Cardiovascular measurement (ECG) during a script-driven imagery (SDI) is a promising method for testing in a RCT.

H3: The study will demonstrate that it is feasible to recruit participants and that at least 80% of them complete the intervention and the study

H4: Participants' reflections will generate new knowledge concerning trauma treatment evaluation identifying relevant primary outcome measures for a larger-scale RCT study.

3. Approach

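### One small dataset may both choose the RCT's primary outcome and supply its effect size, and nothing in the protocol guards against choosing on observed change

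*Protocol*

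**What the plan says.** Section 2 gives Study C this aim: "To establish foundational data, methodologies, and effect sizes for a subsequent full-scale RCT". RQ3 lists five self-report domains: "PTSD symptoms, sexual satisfaction, sexual shame, interoceptive awareness and reactions to touch from pre intervention to post-intervention and at a 3-month follow-up". Section 3.1 adds responses to script-driven imagery (RSDI) and two ECG indices (RMSSD and sample entropy), which makes eight candidate measures before subscales and time points are counted. None is named as the lead outcome, and section 3.1 (Data analysis) applies no multiplicity correction. The planned sample is two groups of ten women.

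Two statements bear on how the RCT's primary outcome will be found. H4 reads: "Participants' reflections will generate new knowledge concerning trauma treatment evaluation identifying relevant primary outcome measures for a larger-scale RCT study". The Data analysis part of section 3.1 says of the thesis's conclusions: "These conclusions will inform the design of a future RCT, including power calculations, as well as primary outcomes".

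The reflections that H4 relies on come from RQ6, which asks how participants interpret their quantitative data, "with a specific focus on data that stands out or are unexpected in relation to their lived experiences". Section 3.1 (Data collection, Study C) repeats the emphasis: "focusing on how they understand quantitative data that stands out or are experienced as unexpected". The design is explanatory sequential, so the scores are analysed before the interviews, and the activity table in section 3.4 lists the steps in that order.

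The protocol does not separate the data that guide the choice of outcome from the data that give its effect size. It also mentions no minimal important difference, confidence limit or shrinkage for the RCT power calculation.

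**The concern.** When several noisy estimates are available and the choice among them depends even partly on their size, the chosen estimate is biased upwards. With about 20 women the noise is large: the 95% interval for a standardised mean change has a half-width of about 0.47. A trial sized on a change picked this way is too small. This would be so even in a perfectly controlled pilot of the same size.

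The interview focus adds a second problem. Women are asked mainly about scores that stand out, so a measure that matters to them but gave an unremarkable result may get little reflection and be overlooked as a candidate.

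The stake is the RCT that this study exists to prepare. An underpowered RCT could wrongly dismiss a useful treatment.

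**Working it through.** The protocol gives no effect size, SD or power figure, so there is nothing of its own to reproduce. The check asks how much harm selection on observed change could do.

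**Inputs from the protocol:** n=20 (section 3.1, Recruitment); five self-report domains (RQ3); two-sided 0.05 (Data analysis); a possible third group (Potential weaknesses and risks), taken here as n=30 because its size is not stated.

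**Assumptions not in the protocol:** every outcome has true standardised change 0.40; common correlation ρ from 0.3 to 0.7; RCT power of 80%; the observed pre–post change is used directly as the RCT difference.

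**Step 1: RCT size if the truth were known.** n per arm = 2(1.96 + 0.8416)² / d² = 15.70 / 0.16 = 98.1, so 99.

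**Step 2: size of the largest of five, by hand.** The expected maximum of five standard normal values is 1.163, and the standard error of the change is about √(1/20) = 0.224. The expected largest change is about 0.40 + 1.163 × 0.224 × √(1−ρ), which is 0.62, 0.58 and 0.54 for ρ = 0.3, 0.5 and 0.7. Simulation (40,000 draws per setting) gives 0.67, 0.63 and 0.58. It is slightly higher because the SD is also estimated from 20 women.

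**Step 3: true power of an RCT sized on the picked change.** In each draw, n per arm = 15.70 / d², and true power = Φ(0.40√(n/2) − 1.96). For example, the median n of 38 at ρ = 0.3 gives Φ(0.40√19 − 1.96) = Φ(−0.22) = 41%. Averaging over all draws, some of which give much larger trials, yields 46%.

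| How the outcome is chosen (n=20) | ρ | Mean observed change | Median n per arm | Mean true power |
|---|---|---|---|---|
| Named beforehand | 0.3–0.5 | 0.41–0.42 | 96 | 73% |
| Largest change | 0.3 | 0.67 | 38 | 46% |
| Largest change | 0.5 | 0.63 | 42 | 50% |
| Largest change | 0.7 | 0.58 | 49 | about 55% |
| Either of the top two | 0.3–0.5 | 0.56–0.59 | 48–53 | 54–57% |
| Largest half the time, otherwise random | 0.3–0.5 | 0.52–0.54 | 54–60 | 59–62% |
| Most discrepant, either direction | 0.3–0.5 | 0.45–0.46 | 72–80 | 66–67% |

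**Step 4: separate selection from imprecision.** The pre-named outcome reaches 73% and not 80%, because a point estimate from 20 women is imprecise even without selection. The part due to selection is the gap below 73%: roughly 18 to 27 points in the worst case, and 6 to 7 points when the most discrepant measure in either direction is taken.

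**Step 5: sensitivity.** With n=30, picking the largest gives power of about 50–59%. More candidates make matters worse. With eight measures, true change 0.5, ρ = 0.5 and n=20, the largest averages 0.80. An RCT sized on that average has 15.70 / 0.64 = 24.5, so 25 per arm instead of 63, and true power Φ(0.5√12.5 − 1.96) = Φ(−0.19), about 42%.

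**The case against.** A reader might infer that the measure most favoured by chance will be chosen. The protocol does not say so. H4 places the choice with participants' reflections and with relevance. RQ6 covers results that conflict with lived experience, so a scale that did not move although the woman felt changed, or one that worsened, qualifies as much as a large gain. A particular focus is not an exclusive one, so it cannot be said that quiet measures will never be considered. These points stand, and they are why the figures for the largest change are a worst case and not a forecast.

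Other points stand in part. Under section 3.4, group 1's Study C interviews take place in April 2026, before group 2's follow-up in August, so those interviews cannot respond to results from all 20 women. The conclusions also draw on the Study A interviews, which are not organised around scores. A third group may raise N. To inform a power calculation is not necessarily to take the observed change as the target difference. All of this weakens the link between size of change and choice, but none of it breaks the link. The safeguards under Potential weaknesses and risks (independent therapists, supervisors and statistician) address researcher bias, not selection by chance.

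Finally, the selection rule could be left to the RCT protocol or to an SAP not shown here. That holds for a detailed rule. It does not cover the interview focus or the role Aim 3 gives to effect sizes, because both are choices made in this protocol.

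**Conclusion.** The point holds as an unguarded risk. One small dataset may inform the choice of the RCT's primary outcome and also supply the effect size for its power calculation. The interviews meant to guide the choice lean towards notable results, and no rule stops observed change from deciding it.

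If the largest of five changes were picked and used directly, true power would be about 45–55% at n=20, or 50–59% at n=30, where 80% was intended. Weaker forms of selection lose less. All of these figures rest on the assumed true change, the assumed correlations and direct use of the pre–post change as the RCT difference; none of these comes from the protocol. The stronger reading, that selection on size is planned, is not supported.

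**What to change.** 1. In every Study C interview, ask the same fixed question about whether each repeated measure captures what matters to the woman, whatever its result. Keep the focus on unexpected data alongside it.
2. In Aim 3 and the Data analysis text, state that this study supplies the SD, between-visit correlation, completeness and retention for the RCT power calculation. State also that the target difference is set independently, for example as a minimal important difference, and not taken from the observed change.
3. Before change scores are seen, state that relevance to the women, completeness and floor or ceiling effects are the main criteria for the RCT primary outcome, and that size or significance of change alone does not decide it. Responsiveness may still be considered; barring it entirely would be debatable.

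The cost is a few lines of text, slightly longer interviews and probably a larger planned RCT. Participants' views stay central, as H4 intends, and are heard on every measure.

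### Does a third-group trigger of more than 3 dropouts conflict with the hypothesis that at least 80% of 20 women complete?

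*Protocol*

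**What the plan says.** Section 3.1 (Recruitment of participants) plans two groups of ten women, 20 in all.

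Section 2 (Hypotheses, aims and objectives) states H3: "The study will demonstrate that it is feasible to recruit participants and that at least 80% of them complete the intervention and the study". RQ5 in the same section makes adherence a reported result: "What is the adherence rate (recruitment, dropout, and attendance rates among participants) to the intervention".

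Section 3.1 (Potential weaknesses and risks) describes an early look and its purpose: "To ensure enough participants there will be conducted an interim analysis post intervention". It continues: "A third group will be included in autumn 2026 if there is a larger dropout of women (>3) or less partners (<10) than expected". A third group may also open if the interim analysis shows that a larger sample is needed to design the future trial.

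The protocol does not define dropout, does not link the trigger to H3, and names no test or interval for the completion proportion.

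**The concern.** Two numbers describe acceptable attrition in the same 20 women, and they do not coincide. H3 tolerates 4 non-completers. The top-up rule treats a fourth dropout as more than was expected, which implies an expectation of at least 17/20, or 85%. At exactly 4 dropouts, completion would be as hypothesised and dropout would be worse than expected. The 80% figure is the only numeric criterion in H1 to H4, so an ambiguity there seems to matter for a feasibility study.

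The verb in H3 raises a second worry. It says the study will demonstrate at least 80% completion, yet 16 of 20 is compatible with a true rate well below that. A reader planning the randomised trial could take a pass at 16/20 as firmer evidence than it is. No treatment comparison is at stake on either count.

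**Working it through.** **Inputs.** N = 20 (section 3.1, Recruitment of participants); H3 floor 80% (section 2); dropout trigger >3 (section 3.1, Potential weaknesses and risks). The protocol gives no sample-size calculation for H3, so there is no computed figure to reproduce. The check is a direct count followed by binomial probabilities.

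**Count.** 0.80 × 20 = 16 completers, so at most 4 non-completers. The trigger >3 means 4 or more. For now, treat a dropout as a woman who does not complete in H3's sense.

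| Dropouts of 20 | Completion | H3 met | Trigger fires |
|---|---|---|---|
| 3 | 17/20 = 85% | yes | no |
| 4 | 16/20 = 80% | yes | yes |
| 5 | 15/20 = 75% | no | yes |

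The overlap is the single outcome of 4 dropouts.

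**How often.** Let X be the number completing, X ~ Binomial(20, p), with assumed true completion p.

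| p | P(X = 16) | Trigger fires, P(X ≤ 16) | Share of firings with H3 met |
|---|---|---|---|
| 0.80 | 0.218 | 0.589 | 0.218/0.589 = 37% |
| 0.85 | 0.182 | 0.352 | 0.182/0.352 = 52% |
| 0.90 | 0.090 | 0.133 | 0.090/0.133 = 68% |

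The last column also assumes that H3 is judged on the first 20 women even if a third group opens.

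**What aligning the cut-offs would do.** Moving the trigger to >4 lowers its firing probability, P(X ≤ 15), to 37%, 17% and 4% at p = 0.80, 0.85 and 0.90. Moving H3 to 17/20 lowers the chance of meeting it from 63%, 83% and 96% to 41%, 65% and 87%.

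**Timing.** The look is described as post intervention, whereas H3 also requires completing the study, which runs to the 3-month follow-up. Suppose each remaining woman is lost later, independently, with probability q (an assumption).

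- 16 women left: H3 needs no further loss, (1 − q)^16 = 44% at q = 0.05 and 19% at q = 0.10.
- 17 women left: one loss is allowed, (1 − q)^17 + 17q(1 − q)^16 = 79% at q = 0.05 and 48% at q = 0.10.

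Four dropouts at the look therefore need not mean that H3 is met.

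**Strength of 16/20.** The exact (Clopper-Pearson) two-sided 95% interval is 56.3% to 94.3%. The choice of interval is an assumption, since the protocol names none for completion. A result of 16/20 or better has probability 24% at a true rate of 70% and 41% at 75%. Only 20/20 has an exact lower limit above 80% (83.2%); 19/20 gives 75.1%.

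**The case for a change.** The best case for a change is that the rule justifies its cut-off by what was expected, not by a minimum number needed for analysis. The only other numeric completion figure in the protocol is H3's 80%, and nothing explains why the two differ. If true completion sits exactly at H3's level, the trigger is more likely than not to fire (59%), so dropout would be labelled excessive at the very rate the study hypothesises as its floor. If a third group of ten opens (its size is an assumption), the denominator becomes about 30 and H3's allowance becomes 6, and the protocol does not say which denominator applies. The feasibility conclusions are also meant to inform the design of the randomised trial, so over-reading 16/20 could carry forward.

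The arithmetic stands, and the text would be clearer with a definition of dropout, a sentence saying the trigger is stricter than H3, and a named denominator. The claim of a contradiction does not stand. Expecting 85% or better while setting a floor of 80% is coherent, and a stricter trigger suits a rule meant to secure enough participants. As for the verb, H3 is listed as a hypothesis and concerns the proportion of these participants. It states no test of a population rate, and the reporting of an interval is commonly left to an analysis plan that is not shown here.

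One point against the timing argument should be granted. Group 2's follow-up is scheduled for August 2026 and the third group for autumn 2026. If the decision waited until all follow-up was in, the margin for later loss would no longer be needed. The distinction between a floor and a safeguard would remain.

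**Conclusion.** No change is needed. The cut-offs differ by one woman and overlap only at 4 dropouts of 20, an outcome with probability 9% to 22% for true completion between 90% and 80%. In that outcome both rules can be applied as written: a third group opens, and 16/20 is reported as meeting H3 if no one is lost later and the first 20 women are the denominator. Neither rule then gives a wrong result.

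Aligning the numbers brings no clear gain. A trigger of >4 would leave 16 women with no slack for follow-up loss and no top-up; an H3 floor of 17/20 is simply harder to meet. Both are debatable trade-offs.

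What remains is missing explanation: what counts as dropout, why the trigger is stricter, and which denominator judges H3. An analyst can settle these sensibly by reporting completion of the intervention and of the study with an exact interval, and by showing the first 20 women apart from any third group. The conclusion rests on reading H3 as a prediction about the observed proportion. If it were offered as proof that the underlying rate is at least 80%, 16/20 would not support it.
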